6.6. Safety Summaries and Analyses

Safety summaries will be based on the SAS.

6.6.1. Adverse Events

Listings and summary tables of adverse events will be based on the SAS.

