1. VERSION HISTORY

This CSR Statistical Analysis Plan (SAP) for study **C0221002** is based on **Protocol Amendment 5** dated **18-Aug-2021**.

Table 1. Summary of Changes

Version/ Date	Associated Protocol Amendment	Rationale	Specific Changes
2 08 FEB 2023	5 18 Aug 2021	Updates to minor components of analysis due to recent FDA guidance, CCI	
 • CCI [REDACTED] • further clarification on analysis and presentation of multiple dose levels; • inclusion of robust standard error estimation included in SAS code due to updated FDA guidance on controlling for covariates in randomized controlled trials; • update sample SAS code due to incorrect coding in previous version; • update to language on missing values being imputed by MMRM; • CCI [REDACTED]
2 08 FEB 2023	5 18 Aug 2021	Changes needed based on Protocol Amendment 5	
 • Updated study objectives, study design and statistical methods to extend treatment duration from 12 weeks to 24 weeks, and to add an optional cohort (Cohort 3) to potentially explore a higher dose of PF-06730512 CCI [REDACTED] in subjects with FSGS, based on emerging data from the study.
2 08 FEB 2023	4 12 Jun 2020	Changes needed based on emerging data to incorporate into IA1 and align with current IA Charter	
 • Included PPAS analysis into IA readouts due to emerging discontinuations in the study (Section 4.2, 6.1.1.2 and Appendix 1.1). • Added predictive probability table related to first morning void sensitivity analysis as was required based on IA Charter (version 1.0) (Section 6.1.1.2 and Appendix 1.1). • Added safety summaries that may be required at IA2 and/or IA3 due to potential need for internal business decision making or external briefing documents (Section 6.5). • Clarified definition of baseline UPCR in case of scenario where Week -1 values were missing (Section 3.1.1).

			
• CCI [REDACTED]• Updated study objectives and study design to align with current protocol (Section 2.1.3 and 2.2) and removed any mention of “Part B”.• Clarified minor points for individual profile plots (Section 6.1.1.1).• Updated demographic tables as required for IA readouts (Sections 6.4.2 and 6.4.3).• Note: Minor formatting issues were identified during QC performed after 22 Dec 2020 final draft version and were the only edits incorporated after database snapshot for IA1.• Included clinical output assessments, PK, ADA/Nab.

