2.2. Study Design

The adaptive study consists of a Screening Period of up to 43 days, an approximately 8-week Lead-in Period, an Investigational Treatment Period of up to 24 weeks during which subjects will receive PF-06730512 once every 2 weeks (Q2W), followed by an approximately 9-week

[figure not shown]
Follow-up Period. Delays to the beginning of Lead-in or Investigational Treatment Period (up to 1 week from visit window specified) due to pending primary or repeat laboratory results that are submitted for analysis within the protocol specified window, will not be considered protocol deviations.

Figure 1. Schematic of the Study Design

Upon commencement of active treatment with PF-06730512, subjects will be dosed intravenously Q2W for up to 24 weeks, but the primary endpoint result will be based on UPCR from a 24-hour urine collection at Week 13. There will be a maximum of 12 infusions of PF-06730512 within the 24-week Investigational Treatment Period. Subjects enrolled prior to Amendment 5 of the protocol will be dosed for 12 weeks with a maximum of 6 infusions of PF-06730512 within a 12-week Investigational Treatment period. Telephone contact visits will be conducted the weeks in between dosing visits to check the subject's overall status, including new or worsening adverse events, changes to concomitant medications, compliance with appropriate contraceptive use, and reminders about upcoming urine collections, when applicable.

CCI

timepoints, according to the Schedule of Activities.

[figure not shown]
The duration of study participation will be up to approximately 11 months from Screening to the last post-treatment Follow-up Period visit. The durations of the study periods are listed below:

- Screening Period up to 43 days;
- Lead-in Period: approximately 8 weeks;
- Investigational Treatment Period: up to 24 weeks (up to 12 weeks for subjects enrolled prior to Amendment 5);
- Follow-up Period: approximately 9 weeks (after last dose given at visit Week 11 or 23).

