3.4. Safety Endpoints

3.4.1. Adverse Events (AEs)

An adverse event is considered treatment emergent relative to a given treatment if:

- the event occurs for the first time during the Investigational Treatment Period and was not seen prior to the start of treatment (during the Lead-in Period), or
- the event was seen prior to the start of treatment but increased in severity during treatment.

Adverse events occurring during the Lead-in Period are considered non-treatment emergent. Events that occur during the Follow-Up Period will be counted as treatment emergent and attributed to the previous treatment taken.

A 3-tier approach for summarizing AEs will not be used for this study as a placebo or active comparator arm is not included in the design and there is a low number of subjects planned to be enrolled.

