5.3.2. Summary Analyses for Categorical Data

Categorical variables will be presented using summary statistics: number of observations, counts and percentages in each category.

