6.5.4. Discontinuations

Subject discontinuations, temporary discontinuations or dose reductions due to adverse events will be detailed and summarised by dose (if applicable) and will be based on the respective SAS.

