6.6.2. Laboratory Data

Laboratory data will be listed and summarized by dose. Baseline is as defined in Section 3.5.2.

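### SAP 6.6.1 sets no common window and no observation-time summary for AE tables that mix 12-week and 24-week regimens, so crude TEAE percentages by dose can partly reflect length of observation (minor)

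*SAP*

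**What the plan says.** The whole of SAP 6.6.1 is one sentence: "Listings and summary tables of adverse events will be based on the SAS". SAP 4.3 defines that set as every enrolled subject who received at least one dose, so it contains both regimens.

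The regimens differ in planned length. SAP 2.2 states: "Subjects enrolled prior to Amendment 5 of the protocol will be dosed for 12 weeks with a maximum of 6 infusions of PF-06730512". Later subjects are planned for up to 12 infusions over 24 weeks. The same section fixes the tail: "Follow-up Period: approximately 9 weeks (after last dose given at visit Week 11 or 23".

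SAP 3.4.1 carries the treatment-emergent definition through that tail: "Events that occur during the Follow-Up Period will be counted as treatment emergent and attributed to the previous treatment taken". Protocol 8.1.4 collects AEs for at least 70 ± 7 days after the last dose.

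On presentation, SAP 5.3.2 sets the default: "Categorical variables will be presented using summary statistics: number of observations, counts and percentages in each category". Section 6.6.1 does not say that AEs are shown by dose, but the sections around it do. SAP 6.5.4 summarises AE-related discontinuations by dose. SAP 6.6.2 reads "Laboratory data will be listed and summarized by dose", and 6.6.3 to 6.6.5 follow the same pattern.

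Elsewhere the SAP does separate the two groups of subjects. Section 6.2.3.1 marks enrolment before or after Amendment 5 in the PK listing, summaries and plots, and 6.1.1.1 uses line style to do so in the individual UPCR plots.

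**The concern.** A treatment-emergent definition exists. What is missing is a window of common length, or any summary of how long subjects were observed. Each subject's window runs to a fixed interval after that subject's own last dose, so it is about 12 weeks longer on the 24-week regimen.

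Cumulative incidence rises with time. A dose with more 24-week subjects can therefore show a higher percentage with TEAEs even if the drug does nothing. Cohorts are enrolled in sequence without randomisation (Protocol 3.1, 5.1), so dose follows calendar time and regimen is likely to follow dose. No visible AE table shows observation time or regimen. Safety is a secondary objective and there is no placebo arm, so these tables carry most of the safety reading.

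**Working it through.** The documents state no AE rate or exposure figure, so there is no planned figure to reproduce. The check has four steps.

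**1. Planned observation time.** Dosing every 2 weeks from Day 1 puts infusion 6 on Day 71 and infusion 12 on Day 155 (Schedule of Activities).
- Nine weeks after last dose (SAP 2.2): Day 71 + 63 = Day 134 and Day 155 + 63 = Day 218, that is 133 and 217 days from Day 1, or 19 and 31 weeks.
- Seventy days after last dose (Protocol 8.1.4): Day 141 and Day 225, that is 140 and 224 days, or 20 and 32 weeks.

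The ratio of observation time is 31/19 = 1.63 or 32/20 = 1.60. These are planned maxima before any early discontinuation.

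**2. Does the mix differ by dose?** The SAP version history describes the Amendment 5 update as made "to extend treatment duration from 12 weeks to 24 weeks, and to add an optional cohort (Cohort 3) to potentially explore a higher dose". Cohort 3 therefore came in with the 24-week regimen. For Cohort 1, the first interim analysis needed about 9 completers of the primary assessment (Protocol 9.6). The version history ties the IA1 updates to Amendment 4 and to a December 2020 draft, before Amendment 5 of 18 August 2021. Cohort 1 therefore very likely includes 12-week subjects. SAP 5.2 places IA3 in Cohort 3, while SAP 7.1 calls the IA3 cohort the low dose. Under either label it is a later cohort than Cohort 1. The snapshot date and the final mix are not stated.

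**3. Effect of time alone.** Assumptions: no drug effect, constant hazard, about 22 subjects per cohort, one cohort all on 24 weeks, and a share f of the other on 12 weeks (f from 9/22 to 1). With p8 the assumed 8-week incidence:
- hazard per week: λ = −ln(1 − p8)/8
- incidence over w weeks: I(w) = 1 − exp(−λw)
- ratio = I(long) / [f·I(short) + (1 − f)·I(long)]

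| p8 | I(19) | I(31) | Ratio 19/31, f=9/22 | Ratio 19/31, f=1 | Ratio 20/32, f=9/22 | Ratio 20/32, f=1 |
|---|---|---|---|---|---|---|
| 5% | 11.5% | 18.0% | 1.18 | 1.57 | 1.17 | 1.54 |
| 10% | 22.1% | 33.5% | 1.16 | 1.51 | 1.15 | 1.49 |
| 20% | 41.1% | 57.9% | 1.13 | 1.41 | 1.13 | 1.38 |
| 50% | 80.7% | 93.2% | 1.06 | 1.15 | 1.05 | 1.14 |

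The range is 1.05 to 1.57. At p8 = 10% and 20/32 weeks the percentages are 29.8% versus 34.4% (f = 9/22) or 23.2% versus 34.4% (f = 1), a gap of about 1 to 2.5 subjects of 22.

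**4. What shrinks it.**
- *Dropout.* If 20% of every cohort stop after infusion 3 and are then followed 9-10 weeks (13 or 14 weeks in all), the range becomes 1.04 to 1.49.
- *Early events.* Take an AE with 30% incidence at 140 days. With a Weibull hazard of shape k, incidence at 224 days is 1 − 0.7^(1.6^k): 43.5% for k = 1, 36.3% for k = 0.5 and 33.0% for k = 0.25. The gap falls from 13.5 to 6.3 or 3.0 points. If all events fall in the first 12 weeks, the ratio is 1.0.
- *Equal mix.* The ratio between doses is 1.0.
- *Chance.* For 23.2% versus 34.4% with 22 per cohort, the 95% half-width is 1.96 × √(0.232×0.768/22 + 0.344×0.656/22) = 0.265, about 27 points against a gap of 11.

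**The case against.** The strongest reply is that the harm is inferred. Section 6.6.1 mentions neither dose nor percentages, and the regimen mix by dose is not given. No comparison of AEs between doses is planned: SAP 3.4.1 drops the tiered approach because there is no comparator and few subjects. Sequential cohorts also differ in calendar time and possibly in population, so equalising the window removes only one of several differences. For any one AE term the shift is well inside chance. All of this stands, and it keeps the point minor. It does not close the gap, because longer observation pushes every term, and the row for any TEAE, in the same direction.

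A second reply is that regimen can be recovered. The PK listing carries subject ID and the Amendment 5 marker, so with about 22 subjects per cohort a reader could link it to the AE listing. That is true of the listings. It does not help anyone reading the AE summary tables. Later appendices are largely redacted, so the statement here is confined to visible AE outputs.

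Three stronger readings are tempting and are not supported:
- *The plan will produce a false dose-related safety signal.* The documents give neither the mix nor the AE rates, and the ratio can be 1.0.
- *AE-related discontinuations by dose are inflated by a known factor.* SAP 6.5.4 does not say whether stopping treatment or leaving the study is meant, so the time at risk, and hence any ratio, is not fixed.
- *Comparison of the Lead-in with treatment (Protocol 1.3.1) is distorted by a calculable amount.* SAP 3.4.1 also counts Lead-in events that worsen on treatment. The documents give no basis for that rate, so no figure is offered.

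**Conclusion.** The point holds as a minor reporting gap with a cheap remedy. As written, the AE tables rest on a set whose planned treatment-emergent observation is about 19-20 weeks for some subjects and 31-32 for others, and no visible AE table shows this. If AEs are presented by dose and the mix is uneven, both likely but not stated, time alone gives TEAE ratios of 1.05 to 1.57 under a constant hazard, 5-50% 8-week incidence, and 9/22 to 22/22 of one cohort on 12 weeks. The low share rests on an approximate completer count and a change-log date, so it is not a firm bound. The decision criteria use UPCR and no AE test is planned, so no formal result changes.

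**What to change.** In SAP 6.6.1:

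1. Beside the full TEAE table, add a descriptive by-dose TEAE table limited to Day 1 up to the Week 13 visit, before any Week 13 infusion. Both regimens plan six infusions in that window. Show how many subjects completed it.
2. Report total observation time by dose and by period (Lead-in, treatment, follow-up), so that the AE tables and the discontinuation table in 6.5.4 can be read against it.
3. Flag enrolment before or after Amendment 5 in the AE listings, as the PK listing already does.

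The cost is a few extra small tables from data already collected. The Week 13 table leaves out later events, including the second half of the 24-week regimen, so it must add to the full table and not replace it. Person-time rates could be supportive at most. If events cluster early, the same count gives a rate only 19/31 = 0.61 to 20/32 = 0.63 times as high over the longer window, which misleads in the opposite direction.

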1.3. Rationale

1.3.1. Study Rationale

An “Early Signal of Efficacy” (ESoE) design was chosen to enable the sponsor to relatively quickly identify if PF-06730512 is efficacious in the FSGS patient population prior to expanding the sample size and population to fully demonstrate efficacy and safety that is required for registration. Thus, although the purpose of this phase 2 adaptive study is to evaluate the efficacy, safety, tolerability and pharmacokinetics of PF-06730512 following multiple IV administrations in adult subjects with FSGS, the primary intention is to obtain an early indication of efficacy. Up to 3 doses of PF-06730512 may be assessed in up to 3 separate cohorts.

All subjects will be required to complete an approximately 8-week Lead-in Period prior to receiving treatment with PF-06730512 in the Investigational Treatment Period. The Lead-in Period is designed to:

1. Provide stable baseline data for proteinuria, as measured by urine protein to creatinine ratio (UPCR) and other laboratory and clinical markers of kidney function before subjects receive active treatment, thus enabling potential sensitivity analyses to the primary analysis using internal comparisons.
2. Assist in the interpretation of safety assessments by improving the differentiation of adverse events related to the course of FSGS under standard of care versus adverse events potentially related to investigational product during the Treatment Period.

The Investigational Treatment Period will be 24 weeks in duration.

Given the rarity of the disease and small sample size of the study, a placebo control is not being used. Adequate safety assessment will be feasible based on data obtained in the study’s Lead-in Period in comparison to the Investigational Treatment Period and to historical data from previous clinical studies conducted in FSGS patients.

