8.1.4. Time Period for Collecting AE/SAE Information

The time period for actively eliciting and collecting AEs and SAEs (“active collection period”) for each subject begins from the time the subject provides informed consent, which is obtained before the subject’s participation in the study (ie, before undergoing any study-related procedure and/or receiving investigational product), through and including a minimum of 70 ± 7 calendar days after the last administration of the investigational product.

For subjects who are screen failures, the active collection period ends when screen failure status is determined.

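### The protocol relies on comparing Lead-in with treatment-period safety in place of a placebo, but no adverse-event summary by period is planned

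*SAP*

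**What the plan says.** Protocol 1.3.1 gives the reason for having no placebo: "Given the rarity of the disease and small sample size of the study, a placebo control is not being used". It then says safety can still be assessed adequately using data from the "Lead-in Period in comparison to the Investigational Treatment Period and to historical data from previous clinical studies conducted in FSGS patients". One of the two stated purposes of the Lead-in is to help interpret safety by "improving the differentiation of adverse events related to the course of FSGS under standard of care versus adverse events potentially related to investigational product". Adverse events are therefore collected from consent (Protocol 8.1.4).

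On analysis, Protocol 9.5 plans descriptive safety tables and mentions no Lead-in comparison. SAP 3.4.1 counts an event as treatment emergent if it is new since the Lead-in or has become more severe. It adds: "Adverse events occurring during the Lead-in Period are considered non-treatment emergent". It also states: "Events that occur during the Follow-Up Period will be counted as treatment emergent and attributed to the previous treatment taken". SAP 6.6.1 reads in full: "Listings and summary tables of adverse events will be based on the SAS". Under SAP 4.3 that set contains dosed subjects only.

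Parts of both documents are blacked out, but SAP 3.4.1 and 6.6.1 show no redaction.

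**The concern.** The Lead-in is the only internal reference for safety in a study with no concurrent control, and safety and tolerability is the first-listed secondary objective. Protocol 1.3.1 names the events expected from the disease itself: edema, infections, worsening hypertension and thromboembolism. If these appear in treatment-emergent tables with no background rate beside them, a reader cannot judge whether they exceed what the same patients had before dosing.

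The new-or-worsened rule does not supply that background. It filters events within a subject and does not compare rates. A subject whose Lead-in event recurs more often at the same severity does not meet the definition. A first occurrence that is purely disease-related does. Because the post-dose window is several times longer than the Lead-in, crude counts from the two periods cannot be set side by side either.

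**Working it through.** The documents give no figure for this point, so there is nothing to reproduce. The check is to see where Lead-in data are used, and then how unequal the observation windows are.

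**1. Where Lead-in data are used**

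- UPCR: Lead-in time points are tabulated (SAP 3.2.1 and 6.1.1.1).
- eGFR: Lead-in time points are summarized (SAP 3.2.2).
- Adverse events: the Lead-in enters only through the new-or-worsened rule (SAP 3.4.1).
- Laboratory tests, vital signs, ECG and weight: a single pre-dose Day 1 baseline (SAP 3.4.2 to 3.4.5).
- Historical FSGS data: no use is planned in the visible text.

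**2. Length of the windows**

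- Lead-in: Day -56 to first dose, 56 days (Schedule of Activities).
- After Amendment 5: Day 1 to Day 225, the last follow-up visit. This agrees with the last dose on Day 155 plus 70 days of event collection (Protocol 8.1.4). Ratio 225/56 = 4.0.
- Before Amendment 5: last dose at Week 11, Day 71 (SAP 2.2). Applying the same 70 days gives Day 141. Ratio 141/56 = 2.5. With the roughly 9-week follow-up (63 days) instead, it is Day 134 and 134/56 = 2.4.
- Treatment period alone: 168/56 = 3.0 after the amendment and 84/56 = 1.5 before it.

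**3. What background disease alone would produce**

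Let p be the risk of at least one event of a given type in 56 days. The documents give no value, so p is an assumption, shown over a range. With a constant rate and no drug effect, the chance of at least one event in d days is 1 - (1-p)^(d/56). Under the SAP rule, and ignoring worsening, only subjects free of the event in the Lead-in can contribute. New-onset treatment-emergent incidence is then (1-p) × [1 - (1-p)^(d/56)].

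Example for p = 10% after Amendment 5: 0.90 × (1 - 0.90^4.018) = 0.90 × 0.345 = 0.311.

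| Assumed Lead-in risk p | After Amendment 5 (225 days) | Before Amendment 5 (141 days) |
|---|---|---|
| 5% | 17.7% | 11.5% |
| 10% | 31.1% | 21.0% |
| 20% | 47.4% | 34.4% |
| 30% | 53.3% | 41.5% |

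The ratio to the Lead-in risk runs from 41.5/30 = 1.4 to 17.7/5 = 3.5. In a cohort of 22 at p = 10%, that is 2.2 subjects in the Lead-in against 0.311 × 22 = 6.8 with a treatment-emergent event.

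**4. How closely each period is observed**

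The Lead-in has three visits in 8 weeks (Weeks -8, -4 and -1). The current treatment schedule has 12 dosing visits, a Week 2 visit and 11 telephone contacts, which is 24 contacts in 24 weeks. There is also post-infusion observation of 3 hours after the first three doses and 1 hour after later ones. A rate per patient-month corrects for length of observation but not for this difference in ascertainment.

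**The case against.** Several stronger readings are tempting, and the documents do not support them.

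- A reader might infer that the Lead-in comparison is why there is no placebo. The stated reason is rarity and sample size. The comparison, with historical data, is cited for the adequacy of safety assessment.
- A reader might infer that the SAP merely sets Lead-in events aside. The new-or-worsened rule does use each subject's Lead-in as a reference, although only as a filter.
- A reader might infer that disease-related and drug-related events cannot be separated. Every event carries an investigator causality assessment (Protocol 8.1.5). Lead-in events are recorded, and internal medical experts review accumulating safety data under a plan that is not part of these documents. The comparison remains possible.
- A reader might infer that only treatment-emergent counts will be shown. SAP 6.6.1 refers to adverse events generally, and Appendix 1.1 lists efficacy outputs only, so the safety table layouts are not visible.
- A reader might infer that the dosed set drops people whose Lead-in events stopped them. The progression criteria in Protocol 4.3 are UPCR and eGFR, so this is speculation.

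It can also be said that 1.3.1 promises help with interpretation, not a formal contrast, and that this is a small, open-label, non-pivotal study. SAP 3.4.1 itself drops the tiered adverse-event approach because there is no comparator and few subjects. That is a sound argument against inference, and it rules out a within-subject rate ratio on so few events. The ascertainment difference is also real and would tend to raise the reported rate on treatment.

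What remains is that the protocol names a specific comparison as a basis for adequate safety assessment, and no visible text in either document specifies it.

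**Conclusion.** The point holds as a gap in prespecification. The protocol relies on a Lead-in versus treatment safety comparison that neither Protocol 9.5 nor SAP 3.4.1 and 6.6.1 plans, although the same Lead-in data are tabulated for UPCR and eGFR. Read against Lead-in counts, a crude treatment-emergent table would cover 4.0 times the observation time after Amendment 5 and 2.5 times before it. Background disease alone could then give about 18 to 53% and 12 to 42% new-onset incidence.

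Those percentages rest on an assumed constant risk of 5 to 30% per 8 weeks, no drug effect, complete follow-up and equal ascertainment. They illustrate the distortion and do not predict event rates. The window before Amendment 5 also assumes that the 70-day collection rule applied to those subjects. The gap should be closed, but it does not invalidate the safety data, and a comparison at this sample size can only be descriptive.

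**What to change.** Add one descriptive table to SAP 6.6.1 giving subjects, events and events per patient-month, by preferred term and for serious events. Use separate columns for the Lead-in, treatment and follow-up periods of the dosed subjects, by dose and by enrolment before or after Amendment 5. Omit any within-subject rate ratio.

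Show separately the Lead-in events of subjects who entered the Lead-in but were not dosed, with their own time at risk. Protocol 6.1 classes them as screen failures, and Protocol 8.1.4 says: "For subjects who are screen failures, the active collection period ends when screen failure status is determined". Their events are therefore available, but their follow-up is cut short.

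Label the table as non-concurrent and imprecise (up to about 22 subjects per cohort). State in a footnote that contact is roughly weekly on treatment, with post-infusion observation, against three visits in the 8-week Lead-in, so the reported rate on treatment can be higher with no drug effect. A sentence in the SAP on whether and how historical FSGS data will be used would cover the other half of the protocol's statement.

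The cost is one table programmed from data already collected. The drawback is that sparse Lead-in counts can be over-read, which is why the labels are needed.
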